### Time to First Onset of Event of Interest (EOI) from First Tarlatamab Administration

Time to first onset of EOI will be derived as the number of days from first tarlatamab administration to start date of EOI.

Time to first onset of EOI from first tarlatamab administration (days) = (date of EOI - date of first tarlatamab administration) + 1

Time to first onset of EOI from first tarlatamab administration (hours) = datetime of EOI - datetime of first tarlatamab administration

### Time to First Onset of Event of Interest (EOI) After Each Dose from Last Prior

### Tarlatamab Administration

Time to first onset of EOI will be derived as the number of days from the last prior tarlatamab administration start date to the start date of EOI.

Time to first onset of EOI from last prior tarlatamab administration (days) = (date of EOI - date of last prior tarlatamab administration) + 1

Time to first onset of EOI from last prior tarlatamab administration (hours) = datetime of EOI - datetime of last prior tarlatamab administration

**Treatment-Emergent Adverse Event (TEAE)/Treatment-Related TEAE (TRAЕ)**

Each study will follow their own definition, which are specified in the individual SAPs.

Events that are directly related to lung cancer or disease progression (including, but not limited to, preferred terms “Small cell lung cancer”, “Disease progression” etc.) will be excluded from TEAE analysis.

**4. COVARIATES AND SUBGROUPS**

Not applicable.

**5. ENDPOINT CATEGORIES AND ANALYSES****5.1 Endpoints**

- Exposure to tarlatamab
- Participant incidence of treatment-emergent adverse events (TEAEs)
- Participant incidence of treatment-related TEAEs (TRAEs)
- Electrocardiogram (ECG)
- Clinical laboratory tests
- Physical measurements
- Vital signs

**5.2 Hypothesis/Estimation**

No formal hypothesis testing will be performed.

**5.3 Analysis Subset(s)****5.3.1 Safety Analysis Set**

The safety analysis set is defined as all participants who receive at least 1 dose of tarlatamab. Participants will be analyzed according to the actual dose received. Analysis of all the safety endpoints will be conducted on the safety analysis set.

**5.4 Analysis Methods****5.4.1 General Considerations**

Descriptive statistics will be provided for exposure and safety endpoints. Descriptive statistics on continuous data will include means, medians, standard deviations, Q1, Q3, minimum, and maximum; while categorical data will be summarized using frequency counts and percentages. For time to safety event variables, Kaplan-Meier (KM) estimates and corresponding two-sided 95% confidence interval will be provided.

Data derivation from each study will follow their own principles specified in the individual study SAPs.

Imputation for missing or incomplete data may be performed if required. Incomplete adverse event and death dates will be imputed as described in Appendix A.

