Serious Adverse Event Diagnosis or Syndrome* or Other Safety Finding/Special Situation with a Serious Adverse Event* –

- If the diagnosis is known, it should be entered. Do not list all signs/symptoms if they are included in the diagnosis.
- If a diagnosis is not known, the relevant signs/symptoms should be entered.
- If the event is fatal, the cause of death should be entered and autopsy results should be submitted, when available.
- The entry of death is not acceptable, as this is an outcome.

Date Started* – Enter date the adverse event first started (not the date on which the event met serious criteria) rather than the date of diagnosis or hospitalization. This is a mandatory field.

Date Ended – Enter date the adverse event ended and not the date when the event no longer met serious criteria. If the event has not ended at the time of the initial report, a follow-up report should be completed when the end date is known. If the event is fatal, enter the date of death as the end date.

If event occurred before the first dose of Investigational Product (IP)/drug under study, add a check mark in the corresponding box.

Is event serious?* – Indicate Yes or No. This is a mandatory field.

Serious Criteria Code* – This is a mandatory field for serious events. Enter all reasons why the reported event has met serious criteria:

- Immediately life-threatening – Use only if the subject was at immediate risk of death from the event as it occurred. Emergency treatment is often required to sustain life in this situation.
- If the investigator decides an event should be reported in an expedited manner, but it does not meet other serious criteria, "Other Medically Important Serious Event" may be the appropriate serious criterion.

Relationship to IP – The Investigator must determine and enter the relationship of the event to the IP at the time the event is initially reported. This is a mandatory field.

FORM-494035, Effective Date: 30 Nov 2023, Version: 3.0

Completion Instructions – Clinical Trial Electronic Serious Adverse Event Contingency Report Form
(for use for clinical trial studies using Electronic Data Capture [EDC])

Note, this form is to be used under restricted conditions outlined on page 1 of the form. If you must fax or email an event report to Amgen, you must also enter that event into the EDC system (eg, Rave) when it becomes available.

Relationship to investigational device (Amgen investigational device and/or a non-Amgen investigational device)* –

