**Duration of Adverse Event**

$$\text{Duration of resolved adverse events (days)} = (\text{event end date} - \text{event start date}) + 1$$

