### Time to Adverse Event Resolution

Time to resolution is defined as the interval from the event start date to event end date. Unresolved events are censored at last dose of tarlatamab date + 65 days, end of study date, death date or analysis cutoff date, whichever occurs earlier.

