Additionally, summaries of time to first onset of treatment-emergent EOIs from first tarlatamab administration (days), time to first onset of treatment-emergent EOIs after each dose from last prior tarlatamab administration (days), and duration of treatment-emergent EOIs (days) will be provided. Summaries of time to first onset of treatment-emergent EOIs from first tarlatamab administration (hours), and time to first onset of treatment-emergent EOIs after each dose from last prior tarlatamab administration (hours) will be provided for CRS (AMQ Narrow) only. Summaries of treatment-emergent CRS (AMQ Narrow) by dose, time from onset of grade 1 treatment-emergent CRS (AMQ Narrow) to grade 2 or higher treatment-emergent CRS (AMQ Narrow) by dose, time from onset of grade 1 treatment-emergent CRS (AMQ Narrow) to grade 2 treatment-emergent CRS (AMQ Narrow), duration of treatment-emergent CRS (AMQ Narrow) for participants that required tocilizumab, participant incidence of treatment-emergent CRS (AMQ Narrow) treated with tocilizumab, participant incidence of recurrent treatment-emergent CRS (AMQ Narrow), summary of treatment-emergent CRS (AMQ Narrow) rebound incidence in participants following recommended tarlatamab dosage for restarting therapy after dose delay, participant incidence of intervention utilization in relation to treatment-emergent CRS (AMQ Narrow), participant incidence of intervention utilization within and after 24 hours of last prior dose at cycle 1 day 1 and cycle 1 day 8 for grade 2 or higher treatment-emergent CRS (AMQ Narrow), participant incidence and time to onset for grade 2 or higher treatment-emergent CRS (AMQ Narrow) by dose will be presented, other analyses for CRS (AMQ Narrow) may be provided as well if needed. Participant incidence of treatment-emergent ICANS and associated neurological events by last prior tarlatamab administration, participant incidence of treatment-emergent ICANS and associated neurological events by last prior tarlatamab administration visit and worst grade, participant incidence of recurrent treatment-emergent ICANS and

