#### **5.4.6 Clinical Laboratory Tests**

Shift tables between the worst postbaseline and baseline grades of selected laboratory parameters will be presented. Participant incidence of toxicity change of more than 3 grades from baseline will be summarized. Laboratory abnormalities that worsened from baseline will be summarized by all grades and grade 3 to 4.

Participant incidence of suspected Hy's law cases will be summarized using the following criteria:

- ALT or AST  $> 3 \times$  ULN at baseline and on-study.
- Total bilirubin  $> 2 \times$  ULN at baseline and on-study.
- (ALT or AST)  $> 3 \times$  ULN and (Total bilirubin  $> 2 \times$  ULN) and (ALP  $< 2 \times$  ULN) at baseline and on-study or within 30 days after a postbaseline ALT or AST (transaminases) elevation

Summaries of time from first tarlatamab administration (days) to first onset of grade 3 or higher increased will be provided for ALT, AST and total bilirubin, time from first tarlatamab administration (days) to first onset of grade 3 or higher decreased will be provided for hemoglobin, platelets and total neutrophils.

A listing of ALT, AST, ALP, and total bilirubin values at each time point will be produced for the participants suspected of Hy's law case.

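### Time to adverse event resolution is to be estimated by Kaplan-Meier with death as a censoring date, which overstates the probability that an event resolves

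*SAP*

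**What the plan says.** The general rule is in SAP Section 5.4.1: "For time to safety event variables, Kaplan-Meier (KM) estimates and corresponding two-sided 95% confidence interval will be provided". The SAP names no competing-risk estimator anywhere.

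For one variable the censoring is written out. SAP Section 3, Time to Adverse Event Resolution, measures from event start to event end and then says: "Unresolved events are censored at last dose of tarlatamab date + 65 days, end of study date, death date or analysis cutoff date", whichever comes first.

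For the other time variables the SAP gives only the two dates that bound the interval:

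- Onset from first dose (Section 3): "Time to first onset of EOI will be derived as the number of days from first tarlatamab administration to start date of EOI".
- Onset after each dose (Section 3): "Time to first onset of EOI from last prior tarlatamab administration (days) = (date of EOI - date of last prior tarlatamab administration) + 1".
- First grade 3 or higher laboratory change (Section 5.4.6): listed as a summary, with no rule for participants without the change.
- CRS escalation (Section 5.4.4.2): "time from onset of grade 1 treatment-emergent CRS (AMQ Narrow) to grade 2 or higher treatment-emergent CRS (AMQ Narrow) by dose", again with no rule for episodes that end at grade 1.

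On fatal events, the instructions for the serious adverse event contingency form (Protocol Appendix 4, Figure 11-1) say: "If the event is fatal, enter the date of death as the end date". The same instructions give Resolved and Fatal as separate outcome codes.

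**The concern.** Kaplan-Meier treats a censored person as having the same future chance of the event as those still under observation. That is reasonable for a data cutoff. It is not reasonable for death, because nobody who has died can go on to resolve an event. With death censored, one minus Kaplan-Meier describes a setting in which nobody dies. In relapsed small cell lung cancer that is far from the setting a reader of a safety table has in mind.

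The integrated analysis supports the second-line filing (SAP Section 1). Section 5.5 also uses it to characterise the outcome of CRS and neurotoxicity for a postmarketing requirement. An inflated resolution percentage makes toxicity look more reversible than it is, most of all for events that last weeks or months.

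**Working it through.** The documents state no resolution probability, so there is no planned figure to reproduce. The check is an illustration of the size of the bias.

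**Inputs**

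- Median overall survival after progression: 10 months (Protocol Section 2.1). A range of 6 to 12 months is assumed around it.
- Median time to resolution: 3, 14, 60 and 180 days. These are assumptions; the documents give none.
- Constant hazards for resolution and for death (assumption); 1 month = 30.4375 days.

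**Formulas**

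- Resolution hazard h_r = ln 2 / (median resolution time). Death hazard h_d = ln 2 / (median survival).
- One minus Kaplan-Meier with death censored: 1 − exp(−h_r·t).
- True probability of resolution by t with death competing: h_r/(h_r + h_d) × [1 − exp(−(h_r + h_d)·t)].

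**One case in full** (14-day median, day 65, 10-month survival)

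- h_r = 0.6931/14 = 0.04951 per day; h_d = 0.6931/(10 × 30.4375) = 0.00228 per day.
- One minus Kaplan-Meier = 1 − exp(−3.218) = 96.0%.
- Cumulative incidence = (0.04951/0.05179) × [1 − exp(−3.366)] = 0.956 × 0.965 = 92.3%.
- Excess: 3.7 points.

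**All cases**

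| Median resolution | Read at | 1 − KM | Cumulative incidence, survival 10 mo (6 to 12 mo) | Excess in points, 10 mo (12 to 6 mo) |
|---|---|---|---|---|
| 3 days | day 65 | 100.0% | 99.0% (98.4 to 99.2) | 1.0 (0.8 to 1.6) |
| 14 days | day 65 | 96.0% | 92.3% (90.0 to 92.9) | 3.7 (3.1 to 6.0) |
| 60 days | day 180 | 87.5% | 76.6% (70.5 to 78.3) | 10.9 (9.2 to 17.0) |
| 180 days | day 180 | 50.0% | 42.0% (37.7 to 43.2) | 8.0 (6.8 to 12.4) |

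**A check without hazards.** Suppose 5 of 100 events end in death, the other 95 resolve, and the last observation is a resolution. Kaplan-Meier with deaths censored reaches 100% resolved; the true figure is 95%.

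The direction does not depend on the assumptions. With death censored, one minus Kaplan-Meier is never below the cumulative incidence. Only the size does.

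**The case against.** **No listed output.** No table named time to resolution appears in Sections 5.4.4 to 5.5. The listed outputs are durations, which Section 3 defines for resolved events only. This is true, and it limits the reach. But a censoring rule for unresolved events has no use except in a Kaplan-Meier summary under Section 5.4.1, so the plan should be read as intending one.

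**Low stakes.** Section 5.2 rules out formal testing, so no error rate or power is affected. For CRS that resolves in days the gap is about 1 point. Both statements stand.

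**Onset and CRS escalation.** A reader might infer that Kaplan-Meier also overstates how many participants develop a toxicity, or how often CRS escalates. The documents do not support this. They give no censoring rule for those variables, and Section 5.4.1 leaves derivations to study SAPs that are not among the documents. A summary restricted to participants who had the event would be a conditional time, not a probability. Occurrence of toxicity is reported as crude participant incidence and exposure-adjusted rates, which Kaplan-Meier does not touch. Any figure for bias here would rest on a rule and hazards that the reader supplies.

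**Fatal events.** A reader might also infer that fatal events will be counted as resolved, because their end date is the date of death. That is a possible misreading, not a stated rule. The instruction belongs to a contingency form, which has a separate code for a fatal outcome. However, the SAP definition runs to the event end date without mentioning outcome, and SAP Appendix A resets an imputed stop date that falls after death to the death date. One sentence in the SAP would exclude the misreading.

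**Conclusion.** The point holds for time to adverse event resolution. The SAP censors at death and applies Kaplan-Meier, and that combination overstates the probability of resolution. At a 10-month median survival the excess is about 1 point for events lasting days, about 4 points at day 65 for a 14-day median, and about 8 to 11 points at day 180 for medians of 60 to 180 days. These sizes rest on constant hazards, on assumed resolution speeds, and on a background survival figure that may differ from the mortality of the pooled treated participants during adverse event follow-up.

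For onset variables and grade 1 to grade 2 or higher CRS, the finding is only that the SAP leaves the handling of participants without the event unstated. The issue is modest because the analyses are descriptive, but it is worth correcting before the tables are produced.

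**What to change.** 1. In SAP Section 3, Time to Adverse Event Resolution, take the death date out of the censoring list. Define death before resolution, and on or before the other listed dates, as a competing event. The tie rule matters because death is itself a reason for leaving the study (Protocol Section 7.2.1), so the two dates can coincide.
2. Add that an event with a fatal outcome is coded as that competing event and never as resolved, whatever end date is entered or imputed.
3. In Section 5.4.1, for this variable, replace Kaplan-Meier with the Aalen-Johansen cumulative incidence of resolution and its 95% confidence interval.
4. For the onset variables (Sections 3 and 5.4.6) and for CRS escalation (Section 5.4.4.2), state how participants without the event are handled and when they are censored. If a time-to-event estimate is used there, take the same approach: death as the competing event and, for escalation, resolution at grade 1 as well.

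The cost is SAP wording and a standard procedure; no new data are needed. The downside is that reported resolution percentages become slightly less favourable.

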#### **5.4.2 Participant Accountability**

The number and percent of participants who were enrolled, received tarlatamab, completed tarlatamab, discontinued from tarlatamab (including reasons for discontinuing), completed study and discontinued study (including reasons for discontinuing) will be summarized.

#### **5.4.3 Exposure to Tarlatamab**

Descriptive statistics will be produced to describe the exposure to tarlatamab. Number of doses of tarlatamab, cumulative dose (mg), relative dose intensity and treatment duration (weeks) will be summarized. Treatment duration (months) will be summarized for  $\geq 3$ ,  $\geq 6$ ,  $\geq 9$  and  $\geq 12$  months. Additionally, a listing of the delay of tarlatamab administration will be provided.

#### **5.4.4 Adverse Events**

##### **5.4.4.1 All Adverse Events**

The MedDRA version **27.0** or later will be used to code all events categorized as adverse events to a system organ class and a preferred term. The severity of each adverse event will be graded using CTCAE version 5.0 for study 20200491 and tarlatamab arm of study 20210004. The severity of each adverse event for monotherapy cohorts of study 20160323 will be converted from CTCAE version 4.0 to 5.0 where possible. CRS and ICANS events from study 20200491 and tarlatamab arm of study 20210004 are graded according to ASTCT 2019. CRS and ICANS events from monotherapy cohorts of study 20160323 will be converted from Lee et al. 2014 to ASTCT 2019 where possible.

The participant incidence of adverse events will be summarized for all TEAEs, treatment-related TEAEs, serious TEAEs, grade 3 or higher TEAEs, fatal TEAEs, TEAEs leading to dose interruption and/or reduction of tarlatamab and TEAEs leading to discontinuation of tarlatamab.

Worst grade is derived as the maximum grade (per the applicable grading scale CTCAE / ASTCT) for each preferred term per participant.

Detail on the derivation of worst grade at event level will be provided in the TFL shell document.

Participant incidence of all TEAEs and TRAEs will be summarized as outlined in the [Table 3](#). When applicable, rows are sorted by system organ class (alphabetically) and

preferred term within system organ class (in descending order of frequency).

Overall summary of exposure-adjusted event rate of all TEAEs, serious TEAEs, grade 3 or higher TEAEs, fatal TEAEs, TEAEs leading to dose interruption and/or reduction of tarlatamab and TEAEs leading to discontinuation of tarlatamab will be produced. A separate overall summary of exposure-adjusted event rate of serious TEAEs will be provided.

Listing of TEAEs, listing of deaths during the studies will be produced with all the relevant fields.

Events that are directly related to small cell lung cancer/disease progression are excluded in analysis of integrated summary of safety for all TEAEs and TRAEs summaries above because these are not considered as TEAEs. These events are identified by Global Safety Officer using preferred terms coded MedDRA version **27.0** or later. Additional overall summary of TEAEs including events of small cell lung cancer/disease progression, participant incidence of all TEAEs including events of small cell lung cancer/disease progression by preferred term, participant incidence of fatal TEAEs including events of small cell lung cancer/disease progression by system organ class and preferred term will be summarized.

Table 3. TEAE Summary

	Overall	Preferred Term	System Organ Class and Preferred Term	System Organ Class Preferred Term and Worst Grade
Overall summary of TEAEs/TRAEs	x			
All TEAEs		x	x	x
Serious TEAEs		x	x	
Grade 3 or higher TEAEs		x	x	
Fatal TEAEs		x	x	
TEAEs leading to dose interruption and/or reduction of tarlatamab		x	x	
TEAEs leading to discontinuation of tarlatamab		x	x	
TEAEs occurring in $\geq 5\%$ of participants		x		
All TRAEs		x		
Serious TRAEs		x		
Grade 3 or higher TRAEs		x		
Fatal TRAEs		x		
TRAEs leading to dose interruption and/or reduction of tarlatamab		x		
TRAEs leading to discontinuation of tarlatamab		x		
TRAEs occurring in $\geq 5\%$ of participants		x		

#### 5.4.4.2 Event of Interest (EOI)

EOIs identified for tarlatamab:

Cytokine Release Syndrome (AMQ Broad), Cytokine Release Syndrome (AMQ Narrow), Neutropenia (AMQ Broad), Neutropenia (AMQ Narrow), Immune effector Cell Associated Neurotoxicity Syndrome (ICANS) and associated neurological events (AMQ Broad), Neurological Events [Nervous system disorders (SOC) / Psychiatric disorders (SOC)], Hypersensitivity **broad** events [Hypersensitivity (SMQ Broad) / Anaphylactic reactions (SMQ Narrow)], **Hypersensitivity narrow events [Hypersensitivity (SMQ Narrow) / Anaphylactic reactions (SMQ Narrow)]**.

For the list of EOIs mentioned above, the participant incidence of treatment-emergent adverse events of interest (Amgen MedDRA Queries), grade  $\geq 2$ , grade  $\geq 3$ , grade  $\geq 4$ , serious, fatal, events leading to dose interruption and/or reduction of tarlatamab and events leading to discontinuation of tarlatamab will be summarized.

Summary of all treatment-emergent EOIs, treatment-emergent serious EOIs, grade 3 or higher treatment-emergent EOIs, treatment-emergent fatal EOIs, treatment-emergent EOIs leading to dose interruption and/or reduction of tarlatamab and treatment-emergent EOIs leading to discontinuation of tarlatamab by their categories and preferred term will be provided. Similar summaries will be repeated for treatment-related treatment-emergent adverse events of interest.

Additionally, summaries of time to first onset of treatment-emergent EOIs from first tarlatamab administration (days), time to first onset of treatment-emergent EOIs after each dose from last prior tarlatamab administration (days), and duration of treatment-emergent EOIs (days) will be provided. Summaries of time to first onset of treatment-emergent EOIs from first tarlatamab administration (hours), and time to first onset of treatment-emergent EOIs after each dose from last prior tarlatamab administration (hours) will be provided for CRS (AMQ Narrow) only. Summaries of treatment-emergent CRS (AMQ Narrow) by dose, time from onset of grade 1 treatment-emergent CRS (AMQ Narrow) to grade 2 or higher treatment-emergent CRS (AMQ Narrow) by dose, time from onset of grade 1 treatment-emergent CRS (AMQ Narrow) to grade 2 treatment-emergent CRS (AMQ Narrow), duration of treatment-emergent CRS (AMQ Narrow) for participants that required tocilizumab, participant incidence of treatment-emergent CRS (AMQ Narrow) treated with tocilizumab, participant incidence of recurrent treatment-emergent CRS (AMQ Narrow), summary of treatment-emergent CRS (AMQ Narrow) rebound incidence in participants following recommended tarlatamab dosage for restarting therapy after dose delay, participant incidence of intervention utilization in relation to treatment-emergent CRS (AMQ Narrow), participant incidence of intervention utilization within and after 24 hours of last prior dose at cycle 1 day 1 and cycle 1 day 8 for grade 2 or higher treatment-emergent CRS (AMQ Narrow), participant incidence and time to onset for grade 2 or higher treatment-emergent CRS (AMQ Narrow) by dose will be presented, other analyses for CRS (AMQ Narrow) may be provided as well if needed. Participant incidence of treatment-emergent ICANS and associated neurological events by last prior tarlatamab administration, participant incidence of treatment-emergent ICANS and associated neurological events by last prior tarlatamab administration visit and worst grade, participant incidence of recurrent treatment-emergent ICANS and

associated neurological events, **summaries of time to first onset of treatment-emergent ICANS from first tarlatamab administration (days), time to first onset of treatment-emergent ICANS after each dose from last prior tarlatamab administration (days), and duration of treatment-emergent ICANS (days)** will be presented. Summaries of time to onset of treatment-emergent EOIs and duration of treatment-emergent EOIs will be provided for grade 2 or higher and grade 3 or higher treatment-emergent EOIs respectively.

Listing of recurrent treatment-emergent CRS (AMQ Narrow) will be produced with all the relevant fields.

Overall summary of treatment-emergent CRS (AMQ Narrow) and treatment-related treatment-emergent CRS (AMQ Narrow), time to first onset of treatment-emergent CRS (AMQ Narrow) from first tarlatamab administration (days), time to first onset of treatment-emergent CRS (AMQ Narrow) after each dose from last tarlatamab administration (days and hours), duration of treatment-emergent CRS (AMQ Narrow) (days), treatment-emergent CRS (AMQ Narrow) by dose, time from onset of grade 1 treatment-emergent CRS (AMQ Narrow) to grade 2 or higher treatment-emergent CRS (AMQ Narrow) by dose, time from onset of grade 1 treatment-emergent CRS (AMQ Narrow) to grade 2 treatment-emergent CRS (AMQ Narrow), **and participants incidence of hospitalization due to treatment-emergent CRS (AMQ Narrow) during cycle 1 day 1 and cycle 1 day 8 doses by grade** among participants who received tarlatamab and were enrolled from monotherapy cohorts of study 20160323 part F and tarlatamab arm of study 20210004 under PA3 with mandatory 6 to 8 hours monitoring post-infusion at cycle 1 day 1 and cycle 1 day 8 and participants who received tarlatamab with more than mandatory 6 to 8 hours monitoring post-infusion at cycle 1 day 1 and cycle 1 day 8 may be summarized side by side if there is sufficient number of participants, other analyses for CRS (AMQ Narrow) may be provided as well if needed.

